1 PROTOCOL SUMMARY

1.1 SYNOPSIS

A Phased Clinical Trial of a Dietary Supplement Kava: Biomarker Title:

Changes and Anxiolytic Effects

Study Description:

Objectives: Primary Objective: To characterize pharmacokinetics of

flavokavain A/B free kava.

Secondary None

Objectives:

Endpoints: Primary Endpoint: Examining the half life of each of the six major

kavalactones.

Secondary None

Endpoints:

Study Population: We will recruit 10 healthy participants. There are no restrictions on

> ethnicity, social background, or gender. All subjects must meet the following criteria at baseline to be eligible for participation in the pharmacokinetic study (a) be between the ages of 18 and 50 years (b)

The University of Florida Clinical Research Center will be used to

enroll participants and conduct research procedures. This facility is

Females of potential childbearing status must use adequate

contraceptive precautions.

Phase:

Description of Sites/Facilities

Enrolling Participants: designed for clinical research.

Description of Study Intervention:

Ten subjects will be recruited and enrolled into the pilot pharmacokinetic study. Each subject will stay in the out-patient Clinical Research Center (CRC) at the CTSI during the 8-h study period. Participants will be asked to refrain from food, liquids other than water, and medications for 12 hours prior to entering the Clinical Research Center of the UF CTSI. They will have an indwelling venous catheter placed in the lower arm to facilitate the multiple blood collections during the study. Each subject will take three 75 mg kava capsules and ten blood draws (2 mL EDTA vacutainer) will be collected corresponding to the absorption, distribution, metabolism and excretion phase of the pharmacokinetic curve. Specifically, blood will be withdrawn at baseline and 0.5, 1, 2, 3, 4, 5, 6, 8, and 12 hours after kava ingestion. The blood samples will be processed and then stored at -80°C till analysis. The period of follow up for any delayed adverse effects (e.g., monitoring of liver function) will be extended such that all participants will be followed for a full 12 weeks after their last kava ingestion.

A Phased Clinical Trial of a Dietary Supplement Kava: Biomarker Changes and Anxiolytic Effects Phase

1: Kava Pharmacokinetics

Protocol PAR-18-829 11 May 2021

Study Duration: 24 weeks **Participant Duration:** 12 weeks

1.2 SCHEMA

Week/Day (-14 to -1)

Screening

- Obtain informed consent
- Screen potential participants by inclusion and exclusion criteria
- Obtain medical history
- Height and weight
- Concomitant medication review
- Lab testing (CMP, PT/INR, Indirect bilirubin, CYP2D6)
- Urine Drug Screen
- Urine Pregnancy test (for women on child bearing potential)
- C-SSRS
- HAM-A

Visit1/Day

Baseline assessments/Study intervention

- Concomitant medication review
- Adverse event review and evaluation
- · Administer study medication
- Urine drug screen
- Urine pregnancy test (for women of child bearing potential)
- PK sampling (pre-dose, 0.5, 1, 2, 3, 4, 5, 6, 8, and 12 hours post dose)
- Lab testing (CMP)

Visit 2/Week 1

- Lab testing (CMP)
- Adverse event review and evaluation
- Concomitant medication review

Visit 3/Week 4

- Lab testing (CMP)
- Adverse event review and evaluation
- Concomitant medication review

Visit 4/Week 8

- Lab testing (CMP)
- Adverse event review and evaluation
- Concomitant medication review

Visit 5/Week 12

Final assessments

- Lab testing (CMP, PT/INR)
- Adverse event review and evaluation
- Concomitant medication review

Version 5.000

1.3 SCHEDULE OF ACTIVITIES (SOA)

Protocol PAR-18-829

| Procedures | | Screening Day -14 to -1 | Baseline Visit 1, Day 1 | 2 | Week 4 Study Visit 3 Day 28 +/- 1 day | Week 8 Study Visit 4 Day 56 +/-1 day | Week 12/Final Visit Study Visit 5 Day 84 +/- 1 day |
|---|---|-------------------------------|-------------------------------|---|---|--|--|
| Informed consent | | X | | | | | 2 447 |
| Demographics | | Х | | | | | |
| Inclusion/exclusion review | х | Х | | | | | |
| Medical History | | Х | | | | | |
| Administer study intervention | | | Х | | | | |
| Concomitant medication review | | X | Х | | | | |
| Height and weight | | Х | | | | | |
| Vital signs | | Х | | | | | |
| CYP2D6 testing | | Х | | | | | |
| Comprehensive Metabolic Panel testing | | Х | X b | Х | X | X | X |
| PT/INR | | Х | | | | | Х |
| Urine pregnancy test ^a | | Х | Х | | | | |
| Urine drug screen | | Х | Х | | | | |
| Adverse event review and evaluation | | | Х | | | | |
| Pharmacokinetic sampling | | | Х | | | | |
| HAM-A | | Х | | | | | |
| C-SSRS | | Х | | | | | |
| Complete Case Report Forms (CRFs) | | Х | Х | X | Х | Х | X |
| a: for women of child bearing potential b: test will be performed at 12 hours post initial kava ingestion | | | | | | | |

2 INTRODUCTION

2.1 STUDY RATIONALE

To determine the pharmacokinetics of flavokavain A/B-free kava in order to determine optimal dosing for a planned study of biomarkers of anxiolysis following kava administration.

2.2 BACKGROUND

There is a critical need for new anxiolytics with novel mechanisms for GAD treatment. GAD is a common, chronic, and impairing psychiatric disorder that affects more than 16 million American adults annually (1). Evidence-based treatments for GAD include selective serotonin reuptake inhibitors (SSRIs), serotonin norepinephrine reuptake inhibitors (SNRI's), serotonin type 1A partial agonists, and benzodiazepines (BZD) (47). Unfortunately, many patients with GAD report only a partial response with these treatments or cannot tolerate their side effects. These patients continue to suffer with high levels of anxiety and impairment throughout their lives. BZDs are of particular concern because they often become the only treatment option for patients with GAD but carry a risk of chemical dependency, tolerance to the therapeutic effects, cognitive impairment, and in the long term, dementia and even death (3). Specifically, there is an unmet clinical need for new anxiolytics with a mechanism different from BZDs and free of the associated adverse effects (4). Kava is a promising candidate as a mechanistically novel anxiolytic. Kava is derived from Piper methysticum, a shrub that grows in the South Pacific islands. Extracts from the roots of this shrub (kava) are traditionally consumed as a daily beverage to help people relax, socialize, and improve sleep quality. Kava was used to treat anxiety in Europe in the 1990s (7-13). Clinical studies have shown that kava is effective for anxiolysis across a variety of patient groups (7-13). A recent meta-analysis of four randomized placebo-controlled trials that examined kava use for GAD favored improvement of anxiety symptoms with kava over placebo, although the results were not statistically significant (standardized mean difference = -0.99, CI -2.12 to 0.14) (14, 15). Importantly, current studies demonstrate no signs of addiction or withdrawal from kava, a clear advantage over the BZDs (23). These results not only suggest that kava is a promising candidate for treatment of GAD, but also clearly indicate that more research is needed to confirm its utility. The mechanisms behind kava's anxiolytic activity are far from established. Several targets have been proposed based on biochemical or cellular results at human irrelevant concentrations without in vivo validation, including GABA_A (17-19), dopamine receptors (18), opioid receptors (18), histamine receptors (18), MAO-B (20), or ion channels (21). A few in vivo studies indicate that kava's anxiolytic effect is not mediated through GABA_A (24, 25), consistent with its lack of addiction or withdrawal in clinic. Given that most of currently available treatments for GAD work via serotonin reuptake or GABAA, this study has the potential to identify an anxiolytic with a unique mechanism of action. Kava use as a dietary supplement is increasing. Kava has long been available as a dietary supplement in the US market with a resurgence recently - the amount of kava exported from Vanuatu, Fiji and Tonga (the major kava producing countries) increased by ~25% annually between 2008 – 2013 and the U.S.A. is a major destination of kava export (30). Quality control and standardization, however, are lacking - we have analyzed the composition of 25 commercial kava products by LC-MS/MS. The abundance of the major kavalactones

varied by 10 – 30 fold (30) despite the fact that these kavalactones have been recommended for standardization (48). These products therefore likely vary significantly in their anxiolytic efficacies. The abundance of the hepatotoxic compounds, flavokavains A and B (32), varies even more (30), such that some products may impose higher risk of hepatotoxicity than others. Rigorous research therefore is needed to characterize kava's pharmacology in conjunction with accurate characterization of its chemical compositions, essential to maximize kava's benefit and to minimize its potential adverse risk. Kava is safe for use in clinical populations, especially when properly prepared. Kava was banned for clinical use in Europe from 2001 – 2014 because of concerns about potential hepatotoxicity (26). However, the purported incidence rate of kava-induced hepatotoxicity is extremely low (0.3 - 1) cases per one million daily doses) (48-56), much lower than BZD-based anxiolytics (57, 58). In addition, the WHO found that kava-related hepatotoxicity was likely due to quality problems, adulteration of the root with other parts of the plant, use of ethanol- rather than water-based extraction, and in some cases, interactions between kava and other drugs/herb preparations or chronic alcohol use (5, 49, 50, 59). As a result of these assessments, the ban on kava use was lifted in 2014, and kava is again available for use in Europe (26). We have closely monitored the safety of kava and its ingredients in all of our studies. We detected no signs of hepatotoxicity when kava was evaluated alone, even at elevated dosages and extended exposures (27-29, 32, 36, 60, 61). This was further supported by the results of our recent study, demonstrating that kava was safe unless co-administered with acetaminophen, due to flavokavains A and B (32), two lipophilic chemicals low in aqueous extracts (30). This finding suggests that the already low rate of potential hepatotoxicity with kava can be further mitigated by the use of preparations that have low (or no) levels of flavokavains A and B, and by excluding patients who are taking medications known to have potential hepatotoxicity. The risk of observing an instance of hepatotoxicity according to the WHO is less than 0.03% in the R61 phase and less than 0.9% in the R33 phase of this study; this risk is further mitigated by our use of flavokavain A/B-free kava.

2.3 RISK/BENEFIT ASSESSMENT

Protocol PAR-18-829

2.3.1 KNOWN POTENTIAL RISKS

The risks of participating in this project include those incurred during the administration of rating scales, blood drawing, and the administration of study medication (kava).

Drawing blood requires venipuncture and is associated with the momentary discomfort of the needle stick. The risks of venipuncture include discomfort at the site of puncture, possible bruising and swelling around the puncture site, rarely an infection and uncommonly faintness.

Potential side effects from the administration of Kava include: excessive sedation if combined with alcohol, rare allergic reactions and rare liver toxicity. The frequency of liver injury in Kava is not known. Based upon reported cases, liver injury due to kava is less than 1:1,000,000 daily doses, and is likely due to the presence of flavokavains A and B in the kava preparation. A few cases of clinically apparent liver injury have been published in the literature. One of the potential risks with kava is an acute liver injury with severe hepatitis ending in fulminant hepatic failure, requiring liver transplantation, or even leading to death. Preliminary data from a previous human study by our group did not identify any adverse events due to the consumption of kava supplementation. In addition, we

Protocol PAR-18-829 11 May 2021

are using a kava preparation that has been rigorously tested for the removal of flavokavains A and B, which are thought to cause the rare cases of liver toxicity that have been observed.

2.3.2 KNOWN POTENTIAL BENEFITS

None

2.3.3 ASSESSMENT OF POTENTIAL RISKS AND BENEFITS

All study personnel are accustomed to maintaining and ensuring patient confidentiality in the course of their work. In addition, all study personnel are highly trained in research procedures and in issues regarding protection of participants' rights and privacy. All members of the research team, including the Pls, coinvestigators, study coordinator, data collectors, research assistants, data manager, and all students associated with the project will complete UF-mandated human subject training prior to study commencement. Participants' identities will be protected through the following measures: consent forms will be stored behind a locked door and in a locked filing cabinet accessible only by the PI, and all identifying information will be stored in a separate, secured location from data that is collected during the study. Access to locked files will be restricted to essential personnel only. In addition to consent and identification files that are secured, all data files will be coded in a manner that makes identification of the participants extremely unlikely. Indeed, participants will be given a numerical ID code to ensure that inadvertent or unauthorized identification does not occur. Data will receive additional layers of security because the whole building, floor, and office in which locked records are maintained have restricted, keyed access. The anonymous codes assigned to participants will be verified and maintained throughout the study, and codes with names will be provided only to meet federal guidelines applicable to the facility. Data will be entered into a REDCap data base developed for the project. REDCap (Research Electronic Data Capture) is a secure, HIPAA-aligned web-based application designed to support traditional case report form data capture. REDCap's automated export procedure will be utilized to export data into a SAS data set for analysis.

The study coordinator for the proposed project has 6 years of experience and will be trained in all study procedures. She will coordinate the screening of potential participants and will meet with [name] weekly to discuss study progress. [name], a gastroenterologist with expertise in hepatology and liver transplantation, will be responsible for overseeing the medical safety monitoring for this trial. He has extensive experience as a medical monitor for national clinical trials of multiple medications. He will communicate with [name] on a regular basis, and will also communicate any and all adverse events to the data safety monitoring board. He will interpret the results of the liver biochemistries (all results will be blinded to treatment condition) and will be responsible for referring participants to appropriate additional clinical evaluation and intervention if needed.

Effective screening will rule out active medical or psychiatric conditions, including supplement or medication use, chronic alcohol use, and evidence of pre-existing liver disease that may prevent someone from participating in the studies. Once the subject enters the study, an experienced research team will closely follow him or her. The research team has developed considerable expertise in monitoring the safety of subjects participating in research studies. An experienced research psychiatrist and the hepatologist is available 24 hours a day, 7 days a week. If at any point in the procedures

Protocol PAR-18-829 11 May 2021

symptoms become distressing or dangerous, subjects will be withdrawn from the study and, if necessary, treatment instituted.

This project will be conducted in compliance with research statutes outlined in the Health Insurance Portability and Accountability Act. Each participant will be assigned a unique identification number, and this number will be used to link all subsequent information collected. This file will be secured with password access, since it represents a direct link between the name and identification number of a participant. All paper files and data are kept in locked file cabinets to ensure confidentiality. The other procedures to ensure confidentiality follow the regulations and policies of the University of Florida and UF Health. Data file archival and back-up will be performed on a regular basis. The routine monitoring, maintenance, and quality control of the databases will be the responsibility of [name]. Participant distress during evaluations: All evaluations have been designed to minimize burden on patients with respect to fatigue, stress and/or discomfort. Only trained individuals will administer study tests and questionnaires. These individuals will be trained to be sensitive to signs of patient fatigue, stress or discomfort. Breaks during testing will be scheduled, and can be initiated by the patient if they desire. Participants may choose whether or not to receive the results of their clinical interviews. Participants who are assessed as suffering from an untreated psychiatric disorder and choose to obtain the results of their interview will be offered referrals to treatment locally if they choose. Participants will be free to discontinue their participation at any time if they feel that it is causing unacceptable distress or discomfort.

Loss of Confidentiality: All research material will be treated in a confidential manner, and only research staff will have access to the data. Confidentiality will be maintained by assigning identification numbers for all aspects of the project; all data entered into computer databases will use only this identifier. Data are kept in separate coded REDCap data sets and in locked cabinets in locked rooms at UF with access limited to a small number of study personnel. All clinical and other records have identifying names of participants and relatives removed. Electronic data will be password protected and stored in a database on a secure server that is also password protected, with no patient identifying information. No identifiable individual data are presented in scientific publications. Only research personnel will have access to this data.

Risks of Treatments of Unknown Efficacy: Participants will be informed by the investigators and through the written consent that few studies exist for kava treatment, and kava for GAD in particular has not been adequately tested.

Emergence of Depressive or other Psychiatric Symptoms or Suicidality: The research team will receive training in the rapid assessment and management of distress or emergence of psychiatric symptoms that may arise during the PK protocol. If a participant's status raises concern, [name] will offer a clinical evaluation and, when appropriate, the study is discontinued, and the participant is referred for treatment according to clinical indication (hospitalization, partial hospitalization, other psychosocial interventions, pharmacotherapy, etc.). If a participant's psychiatric state worsens at any point such that they are no longer able to participate in the treatment, the participant will be withdrawn from the research protocol and referred for the appropriate treatment according to clinical indication. The same procedures apply to any participant who reports suicidal intent or plan or makes a suicide attempt at any point in the study. [name] is a licensed psychiatrist and will provide clinical oversight over assessments of suicidal ideation and safety.

Protocol PAR-18-829

Version 5.000

11 May 2021

Management of psychiatric emergencies: We believe that the risk of psychiatric emergencies occurring during the execution of this study is low, based on the pilot data and because participants are healthy volunteers who have been pre-screened for psychiatric stability. However, should such an emergency arise (such as an acute decompensation, statement or demonstration of active suicidal ideation, violence, etc.), we have procedures in place to ensure the safety of the participant and the staff. Liver function abnormalities: We will use a kava product that has removed the potentially liver toxic elements, flavokavain A and B, and has been rigorously tested for quality. However, we will nevertheless closely monitor serum liver biochemistries (AST, ALT, ALP, bilirubin and albumin) at screening, at hour 12 post-kava ingestion, and at weeks 1, 4, 8 and 12. Although the timing of any potential liver toxicity with kava is not known, the timing of the few reported cases in the NIH liver tox database suggests that the onset of symptoms related to hepatotoxicity (including nausea, fatigue) is likely to be between 2 weeks and 12 weeks following initial ingestion. We will also encourage participants to contact the study team for any concerning symptoms that they may have for up to 6 months post-treatment to ensure that no delayed reactions, no matter how unlikely, are missed. We will carefully educate participants about symptoms to watch for throughout the study and following treatment.

Protocol PAR-18-829 11 May 2021

3 OBJECTIVES AND ENDPOINTS

| OBJECTIVES | ENDPOINTS | JUSTIFICATION FOR ENDPOINTS |
|---|--|---|
| Primary | | |
| To characterize pharmacokinetics of flavokavain A/B-free kava | Examining the half-life of each of the six major kavalactones | This is a standard marker for pharmacokinetics studies |
| Secondary | | |
| None | None | N/A |
| Tertiary/Exploratory | | |
| To characterize plasma cortisol level upon A/B-free kava use | Validate the method and provide pharmacodynamic knowledge of kava on plasma cortisol, which is a biomarker candidate for the biomarker phase of this study | The results will support the studies proposed in the biomarker phase of this study. |

4 STUDY DESIGN

4.1 OVERALL DESIGN

- To develop a pharmacokinetic model to identify the best dose and dosage regimens of flavokavain A/B free kava for its further development as a drug for the treatment of GAD
- Phase 1 Single site study
- Open-label
- An equal number of male and female subjects will be enrolled in study. All races and ethnicities will be included. A dose of supplement kava 225 mg will be administered at baseline either in a single dose or dosed at three times during the study visit. Study group-Pharmacokinetics is a single day intervention with 12 week follow up post study drug ingestion. Ten subjects will be recruited and enrolled into the pilot pharmacokinetic study. Each subject will stay in the out-patient Clinical Research Center (CRC) at the CTSI during the 12 hour study period. Participants will be asked to refrain from food, liquids other than water, and medications for 12 hours prior to entering the Clinical Research Center of the UF CTSI. They will have an indwelling venous catheter placed in the lower arm to facilitate the multiple blood collections during the study. Each subject will take three 75 mg kava capsules and ten blood draws (2 mL EDTA vacutainer) will be collected corresponding to the absorption, distribution, metabolism and excretion phase of the pharmacokinetic curve. Specifically, blood will be withdrawn at baseline and 0.5, 1, 2, 3, 4, 5, 6, 8 and 12 hours after kava ingestion. The blood samples will be processed and then stored at -80°C till analysis. The period of follow up for any delayed adverse effects (e.g., monitoring of liver function) will be extended such that all participants will be followed for a full 12 weeks after their last kava ingestion. CYP2D6 testing will be conducted to determine if the genotype affects the pharmacokinetics of kava.

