5.1 INCLUSION CRITERIA

All subjects must meet the following criteria at baseline to be eligible for participation in the pharmacokinetic study:

- Be between the ages of 18 and 50 years
- Females of potential childbearing status must use adequate contraceptive precautions.

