9.2 SAMPLE SIZE DETERMINATION

We will recruit and screen potential participants until we are able to randomize 10 healthy individuals into the pharmacokinetics phase of this study. As kava pharmacokinetics have never been characterized in humans, this is a pilot study such that, with 10 participants, these results will provide preliminary data of kava pharmacokinetics in humans. The data will be the foundation for future systematic characterization of kava pk in humans.

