9.4 STATISTICAL ANALYSES

9.4.1 GENERAL APPROACH

Plasma concentration-time data of individual kava lactone in will be subjected to non-linear mixed effect modeling (NONMEM). Compartmental modeling approach will be applied to achieve the best fit model on the basis of residual sum of squared error, Akaike's Information Criterion and objective function value. Chi-squared distribution will be assessed to evaluate the significance; e.g. an objective function change (OBJ) of 3.84 is significant at alpha=0.05.

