9.4.5 BASELINE DESCRIPTIVE STATISTICS

Gender, age, percentage of subjects on oral contraceptive, percentage of subjects who take multi vitamins.

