9.4.7 SUB-GROUP ANALYSES

None

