9.4.9 EXPLORATORY ANALYSES

Plasma concentration-time of cortisol levels of all the volunteers will be quantified and tabulated in a csv file to explore the potential effects of kava on the plasma cortisol.

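### Does CYP2D6 testing in a 10-person study need a prespecified genotype analysis and a stricter cut-off than an objective-function change of 3.84?

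*Combined protocol and SAP*

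**What the plan says.** Section 4.1 (Overall Design) closes by stating why genotype is collected: "CYP2D6 testing will be conducted to determine if the genotype affects the pharmacokinetics of kava". The schema (1.2) and the schedule of activities (1.3) place the test at screening.

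Genotype does not appear again where analyses are set out:

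- Section 3 has one primary objective, the pharmacokinetics, measured by the half-life of each of six kavalactones. It has one exploratory objective: "To characterize plasma cortisol level upon A/B-free kava use".
- Section 9.4.1 fits each kavalactone in NONMEM and chooses among compartmental models by residual sum of squares, Akaike's criterion and the objective function. It adds, as an example, that "an objective function change (OBJ) of 3.84 is significant at alpha=0.05". No covariate is named.
- Section 9.4.5 lists the baseline descriptives: "Gender, age, percentage of subjects on oral contraceptive, percentage of subjects who take multi vitamins".
- Section 9.4.7 plans no sub-group analyses.
- Section 9.4.9 covers cortisol only: "to explore the potential effects of kava on the plasma cortisol".

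The eligibility criteria in 5.1 and 5.2 do not select on genotype. On sample size, 9.2 claims only that "with 10 participants, these results will provide preliminary data of kava pharmacokinetics in humans".

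**The concern.** A stated purpose with no matching analysis leaves several choices open until the data are in: how genotypes are grouped, which PK parameter is compared, for which of six kavalactones, and by what rule. The verb in 4.1 promises an answer, while 10 unselected people may include very few carriers of a given genotype. A chance difference, or the absence of one, could then be reported as settled.

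The cut-off seems to make this worse. It is the only significance rule in section 9, so an analyst who tested genotype might reach for it. A drop of 3.84 is the chi-squared 5% point on one degree of freedom, which holds in large samples. A genotype comparison rests on 10 person-level values however many blood samples each person gives, so the true error could exceed 5%. The consequence would be a false genotype effect carried into the dosing model that 4.1 sets out to build.

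**Working it through.** **1. The plan's own figure.** The 95% point of chi-squared on 1 df is 3.8415, and P(chi-squared > 3.84) = 0.0500. The value in 9.4.1 reproduces for one added parameter.

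**2. Size if 3.84 were used for genotype.** Inputs: n = 10 (4.1, 9.2), cut-off 3.84 (9.4.1), two genotype groups (assumed). Take one log PK value per person, normal with equal variance. The likelihood-ratio drop is n·ln(1 + t²/(n − q)), where q is the number of mean parameters.

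- Genotype only, q = 2: t = √(8·(e^0.384 − 1)) = 1.935; two-sided p on 8 df = 0.089.
- Dosing pattern also fitted, q = 3: t = √(7·(e^0.384 − 1)) = 1.810; p on 7 df = 0.113.
- Drop needed for 5%: 10·ln(1 + 2.306²/8) = 5.10, or 10·ln(1 + 2.365²/7) = 5.87 with dosing pattern.

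This is a stand-in for NONMEM, and no NONMEM run was made. A random-intercept simulation with 9 samples per person gives sizes at 3.84 of 4.2%, 4.7%, 6.0%, 7.3%, 8.6% and 8.9% at between-person to residual SD ratios of 0, 0.1, 0.2, 0.3, 0.5 and 1. The documents give no variability, so the ratio is unknown.

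**3. Does the plan make that test?** No. In 9.4.1 the figure follows the choice of compartmental model, is introduced as an example, and is attached to no covariate. Step 2 describes a possible misuse, not a planned step.

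**4. What 10 people can show.** Genotype frequency f, CV and effect size are all assumptions.

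- P(at least 2 carriers among 10) = 1 − (1 − f)^10 − 10f(1 − f)^9 = 9%, 26% and 62% at f = 5%, 10% and 20%.
- Power of a two-sided 5% t test on 8 df uses noncentrality ln(ratio)/(s·√(1/k + 1/(10 − k))), with s = √(ln(1 + CV²)) and k carriers:

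| Carriers : others | True ratio | CV 30% | CV 50% | CV 70% |
|---|---|---|---|---|
| 2 : 8 | 1.5 | 34% | 16% | 11% |
| 2 : 8 | 2 | 74% | 37% | 23% |
| 2 : 8 | 3 | 98% | 73% | 49% |
| 5 : 5 | 2 | 90% | 53% | 33% |

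The 95% interval for the ratio at 2 : 8 extends by a factor exp(2.306·s·√(1/2 + 1/8)) each way: 1.71, 2.37 and 3.16 at those CVs. A large effect could show; a modest one could only be described.

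**5. Would a calibrated cut-off help?** I simulated the step 2 test at 5.10 with no true difference, letting the carriers' SD differ from the others'. With 2 carriers, true size is 0.9%, 5.0%, 12% and 19% when carriers' SD is 0.5, 1, 1.5 and 2 times the others'. With 1 carrier at 2 times it is 26%. The six kavalactones also remain unadjusted: at a true 5% each, and assuming independence, the chance of at least one false positive is 1 − 0.95^6 = 26%.

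**The case for a change.** The strongest case for a change is that the gap is real and cheap to close. Section 4.1 gives the test a purpose, sections 3 and 9 do not carry it through, and a few words would label genotype as exploratory. NONMEM can take a covariate, but the plan names no grouping, parameter or rule, and 3.84 is the only rule on the page. With six kavalactones and two permitted dosing patterns there is room for selective reporting.

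The gap stands, and so does the arithmetic on 3.84 as a hypothetical. The step from there to a defect does not:

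- The entry in 9.4.7 does not contradict 4.1. A genotype covariate in a mixed-effects model is not a sub-group analysis.
- No objective, endpoint or stated decision rests on a genotype result, so a weak one cannot displace a planned conclusion.
- Section 9.2 already limits what may be claimed from 10 people. Read with it, the verb in 4.1 is ordinary wording for why a sample is taken.
- The inflation depends on a variance ratio that the documents do not give, and it disappears when between-person variability is small.

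**Conclusion.** No change to the plan is needed. This is an unwritten analysis that a competent pharmacometrician would fill in the obvious way: tabulate individual PK parameters by genotype and dosing pattern, note how few carriers there are, and draw no firm inference. Softening the verb in 4.1 would do no harm, but it would alter no estimate, test or decision.

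The cut-off is not in error. It is right for one added parameter in model selection, and the plan does not apply it to genotype. The 8.9% (11.3% with dosing pattern fitted) assumes a use that is not planned, a normal model with one value per person, and between-person variability that is not small. Writing 5.10 or 5.87 into the protocol would replace one approximation with another that depends on equal variances in groups of perhaps one or two people.

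The conclusion rests on genotype staying outside the objectives and endpoints and on the report keeping to the pilot status in 9.2. It would change if a genotype result were to decide the dosing regimen for the next phase, which the current text does not say.
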